## 12.2 Secondary End Point

a) *Progression free survival:* It is defined as the time from randomization to the date of the first documented tumor progression (per RECIST v1.1) or death due to anycause. Subjects who die without a reported prior progression will be considered to have progressed on the date of their death. Subjects who did not progress or die will be censored on the date of their last evaluable tumor assessment. Subjects who did not have any on study tumor assessments and did not die will be censored on the date they were randomized. Subjects who started any subsequent anti-cancer therapy without a prior reported progression will be censored at the last evaluable tumor assessment prior to initiation of the subsequent anti-cancer therapy. Progression will be assessed every 6 weeks (from the first on-study radiographic assessment) until disease progression is noted.

b) *Overall survival:* It is defined as the time from randomization to the date of death. A subject who has not died will be censored at last known date alive. OS will be followed continuously while subjects are on the study drug and every 3 months via in-person or phone contact after subjects discontinue the study drug.

c) *Safety and tolerability:* Safety and tolerability objective will be measured by the incidence of adverse events, serious adverse events, deaths, and laboratory abnormalities. Adverse event assessments and laboratory tests are performed at baseline, and continuously throughout the study at the beginning of each subsequent cycle. The safety analysis will be performed in all treated subjects. Descriptive statistics of safety will be presented using

National Cancer Institute (NCI) Common Terminology Criteria for Adverse Events (CTCAE) version 4.0 by treatment arm. All treatment emergent AEs, drug-related AEs, SAEs and drug-related SAEs will be tabulated using worst grade per NCI CTCAE v 4.0 criteria by system organ class and preferred term. On-study lab parameters including hematology, coagulation, chemistry, liver function and renal function will be summarized using worst grade per NCI CTCAE v 4.0 criteria.

d) *Exploratory analysis*: Other exploratory endpoints for include mainly anti-tumor immune response evaluation (tumor adaptive and innate cell immune responses), tumor tissue biomarker analysis, imaging based biomarkers and molecular pharmacodynamics analysis (DNMT1-protein in peripheral blood buffy coat cells and by measurement of plasma CDA enzyme activity by HPLC enzyme assay). These are discussed in detail in section 1.6.

All subjects who signed an informed consent form, randomized and registered for the study will be included in the primary dataset for analyses of baseline characteristics, efficacy and biomarker analysis. All treated subjects, i.e all randomized subjects who received at least one dose of nivolumab or 1 dose of THU-Dec combination will be evaluated for safety and tolerability.

### **13.0 DATA REPORTING / REGULATORY CONSIDERATIONS**

Adverse event lists, guidelines, and instructions for AE reporting can be found in Section 8.0 (Adverse Events: List and Reporting Requirements).

#### **13.1 Data Reporting**

The Overture and OnCore™ Databases will be utilized, as required by the Case Comprehensive Cancer Center, to provide data collection for both accrual entry and trial data management. Overture and OnCore™ are Clinical Trials Management Systems housed on secure servers maintained at Case Western Reserve University. Access to data through Overture and OnCore™ is restricted by user accounts and assigned roles. Once logged into the Overture or OnCore™ system with a user ID and password, Overture and OnCore™ define roles for each user which limits access to appropriate data. User information and password can be obtained by contacting the OnCore™ Administrator at [contact].

Overture and OnCore™ are designed with the capability for study setup, activation, tracking, reporting, data monitoring and review, and eligibility verification. This study will utilize electronic Case Report Form completion in the Overture database. A calendar of events and required forms are available in Overture and OnCore™.

#### **13.2 Regulatory Considerations**

The study will be conducted in compliance with ICH guidelines and with all applicable federal (including 21 CFR parts 56 & 50), state or local laws.

#### 13.2.1 Written Informed consent

Provision of written informed consent must be obtained prior to any study-related procedures. The Principal Investigator will ensure that the subject is given full and adequate oral and written information about the nature, purpose, possible risks and benefits of the study as well as the subject's financial responsibility. Subjects must also be notified that they are free to discontinue from the study at any time. The subject should be given the opportunity to ask questions and be allowed time to consider the information provided. The original, signed written Informed Consent Form must be kept with the Research Chart in conformance with the institution's standard operating procedures. A copy of the signed written Informed Consent Form must be given to the subject. Additionally, documentation of the consenting process should be located in the research chart.

#### 13.2.2 Subject Data Protection

In accordance with the Health Information Portability and Accountability Act (HIPAA), a subject must sign an authorization to release medical information to the sponsor and/or allow the sponsor, a regulatory authority, or Institutional Review Board access to subject's medical information that includes all hospital records relevant to the study, including subjects' medical history.

#### 13.2.3 Retention of records

The Principal Investigator of The Case Comprehensive Cancer Center supervises the retention of all documentation of adverse events, records of study drug receipt and dispensation, and all IRB correspondence for as long as needed to comply with local, national and international regulations. No records will be destroyed until the Principal Investigator confirms destruction is permitted.

#### 13.2.4 Audits and inspections

Authorized representatives of the sponsor, a regulatory authority, an Independent Ethics Committee (IEC) or an Institutional Review Board (IRB) may visit the site to perform audits or inspections, including source data verification. The purpose of an audit or inspection is to systematically and independently examine all study-related activities and documents to determine whether these activities were conducted, and data were recorded, analysed, and accurately reported according to the protocol, Good Clinical Practice (GCP), guidelines of the International Conference on Harmonization (ICH), and any applicable regulatory requirements. For multi-center studies, participating sites must inform the sponsor-investigator of pending audits.

## **APPENDIX I**

### **PERFORMANCE STATUS CRITERIA**

ECOG Performance Status Scale		Karnofsky Performance Scale	
Grade	Description	Percent	Description
0	Normal activity. Full active, able to carry on all pre-disease performance without restriction.	100	Normal, no complaints, no evidence of disease.
		90	able to carry on normal activity; minor signs or symptoms of disease.
1	Symptoms, but ambulatory. Restricted in physically strenuous activity, but ambulatory and able to carry out work of a light or sedentary nature (e.g., light housework, office work).	80	Normal activity with effort; some signs or symptoms of disease.
		70	Cares for self, unable to carry on normal activity or to do active work.
2	In bed < 50% of the time. Ambulatory and capable of all self-care, but unable to carry out any work activities. Up and about more than 50% of waking hours.	60	Requires occasional assistance, but is able to care for most of his/her needs.
		50	Requires considerable assistance and frequent medical care.
3	In bed > 50% of the time. Capable of only limited self-care, confined to bed or chair more than 50% of waking hours.	40	Severely disabled, requires special care and assistance.
		30	Severely disabled, hospitalization indicated. Death not imminent.
4	100% bedridden. Completely disabled. Cannot carry on any self-care. Totally confined to bed or chair.	20	Very sick, hospitalization indicated. Death not imminent.
		10	Moribund, fatal processes progressing rapidly.
5	Dead.	0	Dead

**APPENDIX II**

**SUBJECT CAPSULE DIARY FOR TWICE WEEKLY DOSING**

Add or delete columns and rows and revise the information in *red* as appropriate for the trial.

Subject Name \_\_\_\_\_ Subject Study ID \_\_\_\_\_ Today's date \_\_\_/\_\_\_/\_\_\_  
Drug \_\_\_\_\_ Cycle #: \_\_\_\_\_

**INSTRUCTIONS FOR THE SUBJECT:**

1. Complete one form every **4 weeks** (one treatment cycle).
2. You will take \_\_\_ *number of capsules* of THU 60 minutes before \_\_\_ *number of capsules* of Decitabine on \_\_\_ *day of week* and \_\_\_ *day of week* (twice a week). **Take the capsules with or without food, as you wish.**
3. Record the date, the number of capsules of each drug that you took, and what time you took them.
4. If you have any comments or notice any side effects, please record them in the “Comments” column.
5. Please bring this form and your bottles of THU and Decitabine to your physician when you return for each appointment.
6. Please sign your name at the bottom of the diary.

Day	Date	Time of THU dose	# of capsules taken			Time of Decitabine dose	# of capsules taken			Comments
			___ mg	___ mg			___ mg	___ mg		
1										
2										
3										
4										
5										
6										
7										
8										
9										
10										
11										
12										
13										
14										
15										
16										
17										
18										
19										
20										
21										
22										
23										
24										
25										
26										
27										
28										Add/remove days as needed

**Subject's Signature:** \_\_\_\_\_

**Date:** \_\_\_\_\_

[figure not shown]

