### 3.0 STUDY DESIGN

**3.1 Study design:** This is a Phase 2 randomized two arm trial of nivolumab alone or in combination with THU-Dec, in previously treated patients with stage IV Non-Small Cell Lung Cancer (NSCLC). The primary goal of this trial is to compare the efficacy of oral THU-Dec as a way of enhancing the anti-tumor immune response to nivolumab to that of nivolumab alone. The primary efficacy endpoint is overall RECIST v1.1-defined response. To accomplish this goal 60 patients will be randomized 2:1 to THU-Dec plus nivolumab or nivolumab only respectively.

**3.2 Statistics and Sample size justification:** The primary goal of this trial is to compare the efficacy of immune priming with oral tetrahydrouridine (THU) plus decitabine (THU-Dec) and immune check-point inhibitor nivolumab (THU-Dec+nivolumab) to that of nivolumab alone. The primary efficacy endpoint is overall response. To accomplish this goal 60 patients will be randomized 2:1 to THU-Dec+nivolumab versus nivolumab alone (standard of care) respectively. The purpose of the nivolumab alone arm is to support the notion that the population studied is typical of the general population for which nivolumab has an established response rate of 20%. If the THU-Dec+nivolumab arm has a response rate of 35% or higher, we will consider it worthy of further investigation in a phase III trial. Thus, using a two-stage design (<http://www.swogstat.org/stat/public/twostage.htm>), with  $\alpha = 0.1$  and  $\beta = 0.2$ , we compute that 20 patients will be needed in each of two stages in the THU-Dec+nivolumab arm. If, after the 1st stage of 20 patients in the THU-Dec+nivolumab arm, 2 or fewer respond, the trial will be stopped and the null hypothesis that THU-Dec+nivolumab is no better than nivolumab will be accepted, else the trial continues for an additional 20 patients, at the end of which if 13 or more respond of the 40

patients in the THU-Dec+nivolumab arm, the null hypothesis is rejected and experimental arm of THU-Dec+nivolumab is recommended for further study.

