As an additional exploratory analysis we will compare response rates between treatment groups. We expect a 20% response rate in our control arm of 20 patients. The 95% confidence interval of the proportion  $4/20$  is 7% to 44%. It thus includes our treatment arm expected response rate of 35%. It is therefore very unlikely that our control arm will disprove our assumption that our sample population has a historical response rate of 20%. Thus, to increase the likelihood of gaining some information from our control arm, differences in proportions will be compared between arms. Using a calculator for [two arm binomial studies](#) we compute that the power to detect a difference in rates between our control arm and our treatment arm of 40 patients, assuming one-sided tests,  $\alpha=0.10$  and holding the treatment arm response rate at 35%, is, respectively, 89%, 70%, 50%, 32% and 18% for control response rates of 5%, 10%, 15%, 20%, and 25%. Thus, if our control arm rates are  $<15\%$ , we have  $>50\%$  chance of detecting a difference in response. In addition, we will evaluate the PD-L1 expression in both the control and treatment arm after every 20 patients. If there is  $>10\%$  difference in the PD-L1 status between the groups, we will stratify randomization by PD-L1 status for additional patients to balance the PD-L1 status.

Secondary endpoints include progression-free survival (progression is defined as progression by both RECIST v1.1), overall survival, and toxicity. Progression-free and overall survival will be summarized using the Kaplan-Meier method. Adverse events will be graded using CTCAE version 4.0 criteria, categorized by organ system, and summarized using frequency counts and percentages. With 20 patients treated with nivolumab only and 40 with THU-Dec+nivolumab the probability of observing at least one toxicity of a particular type and/or grade on each arm is 64% and 87%, respectively, if the risk of such an event is 5%, i.e.  $0.64 = (1-0.95^{20})$ .

Methods such as Fisher's exact test, chi-square tests, logistic regression (categorical data), the log-rank test and proportional hazards models (time to event data) will be used to compare patient groups. These analyses are primarily exploratory and it is acknowledged that they will have relatively low statistical power.

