## 8.2 Definitions

### 8.2.1 Adverse Event

An Adverse Event (AE) is defined as any new untoward medical occurrence or worsening of a preexisting medical condition in a clinical investigation subject administered an investigational (medicinal) product and that does not necessarily have a causal relationship with this treatment. An AE can therefore be any unfavorable and unintended sign (such as an abnormal laboratory finding), symptom, or disease temporally associated with the use of investigational product, whether or not considered related to the investigational product.

The causal relationship to study drug is determined by a physician and should be used to assess all adverse events (AE). The casual relationship can be one of the following:

**Related:** There is a reasonable causal relationship between study drug administration and the AE.

**Not related:** There is not a reasonable causal relationship between study drug administration and the AE.

The term "reasonable causal relationship" means there is evidence to suggest a causal relationship.

Adverse events can be spontaneously reported or elicited during open-ended questioning, examination, or evaluation of a subject. (In order to prevent reporting bias, subjects should not be questioned regarding the specific occurrence of one or more AEs.)

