- a) Patients will receive Nivolumab every 2 weeks ( $\pm$  4 days per protocol) (4 weeks i.e 2 treatments=1 cycle) until progression (by RECIST v1.1) or unacceptable toxicity. A treatment break for upto 6 weeks for will be allowed upon discussion with study PI
- b) Patients will be monitored post study every 12 weeks ( $\pm$  3 weeks) for post-study treatment status, clinical safety updates and survival; these could be done by review of patient's medical records or contacting patient's medical provider or the subject.
- c) Patients disease will be monitored with CT scans of the chest, abdomen and pelvis after every 2 cycles (i.e prior to every odd cycle  $\pm$  7 days) or sooner if clinically indicated;
- d) Patients who have recent ( $<$ 6 weeks from start of study treatment) tissue biopsy or patients who have had recurrence after surgery within 6 months of surgical resection may be eligible without a fresh biopsy; Rest of the patients will require a biopsy prior to study enrollment. Patients will require a repeat biopsy in 6-10 weeks post treatment prior to cycle 3 of nivolumab. If the biopsy is felt to be high risk by the treating physician or interventional radiologist, an exception may be made upon discussing with the PI.
- e) For Cycle 1 Day 1 (C1D1) labs, screening labs can be used if  $\leq$ 1 week; pregnancy tests need to be done within 24hrs of first dose.

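### The Appendix II capsule diary asks THU-Dec patients, and by its content only them, to write down side effects, so symptomatic low-grade adverse events may be recorded more fully in that arm

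*Combined protocol and SAP*

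**What the plan says.** Appendix II is headed "SUBJECT CAPSULE DIARY FOR TWICE WEEKLY DOSING". It is one form per four-week cycle with a row for each of 28 days, for the times and numbers of THU and decitabine capsules. Instruction 4 adds: "If you have any comments or notice any side effects, please record them in the “Comments” column". Instruction 5 adds: "Please bring this form and your bottles of THU and Decitabine to your physician when you return for each appointment".

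Section 3.1 sets the arms: "60 patients will be randomized 2:1 to THU-Dec plus nivolumab or nivolumab only respectively", that is 40 and 20 patients. The nivolumab-alone arm takes no capsules.

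For all patients, Section 8.2.1 says: "Adverse events can be spontaneously reported or elicited during open-ended questioning, examination, or evaluation of a subject". It continues: "In order to prevent reporting bias, subjects should not be questioned regarding the specific occurrence of one or more AEs". Section 8.2.3 covers events seen by the clinical team as well as those the patient reports. The Section 10.0 calendar is a single schedule for both arms, with adverse-event review, directed examination, blood count and chemistry at D1 and D15 of each four-week cycle. This follows the infusion schedule ("Patients will receive Nivolumab every 2 weeks").

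Section 2.0 makes the toxicity of the combination a secondary objective. Section 8.2.1 collects all non-serious events, whether or not they are judged treatment-related. Section 12.2(c) presents safety descriptively by treatment arm.

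**The concern.** A daily sheet kept at home and handed to the physician is a standing invitation to note symptoms between visits. One arm has it and the other, as far as the protocol describes, does not. Brief, mild symptoms are the ones most likely to go unmentioned at a visit two weeks later, and they count in the tables because all non-serious events are collected.

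The trial describes no blinding or placebo, and its by-arm tables are the main evidence on what THU-Dec adds to the toxicity of nivolumab. If the diary comments feed the adverse-event record, part of any excess of mild symptoms with THU-Dec could come from fuller recording. Nothing in the plan would let the analyst tell how much, because it does not say how diary comments are handled or ask for the source of an event.

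**Working it through.** **Step 1. Compare the routes by which an event can reach the record.**

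| Route | THU-Dec + nivolumab | Nivolumab alone | Source |
|---|---|---|---|
| Spontaneous report, open-ended questions | yes | yes | 8.2.1 |
| Examination and evaluation at D1 and D15 | yes | yes | 8.2.1, 10.0 |
| Blood count and chemistry at D1 and D15 | yes | yes | 10.0 |
| Written side-effect prompt between visits | yes | none described | Appendix II |

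The arms differ only in the last row. That the diary goes to THU-Dec patients alone is inferred from its content; no sentence says so. Laboratory events are measured alike in both arms, so the question is confined to symptomatic events.

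**Step 2. Look for a link from diary to adverse-event record.** Sections 8.2.1, 8.2.3, 8.4 and 12.2(c) do not mention the diary, and the calendar has no row for it. The only link is instruction 5, which puts the form in the physician's hands. Whether a comment becomes an adverse event is left to staff.

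**Step 3. Illustrate the possible size.** The plan gives no figure to reproduce on this point, and no capture rates. Everything below is assumed: the same true incidence in both arms, 90% capture with the diary, and control capture from 90% (no difference) down to 50%.

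Recorded incidence = true incidence × capture. Artificial gap = true incidence × (diary-arm capture − control capture). The last column is the chance of an exact two-sided Fisher p ≤ 0.05 for 40 v 20 patients when there is no true difference.

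| True incidence | Control capture | Recorded, THU-Dec v control | Gap (points) | Fisher p ≤ 0.05 |
|---|---|---|---|---|
| 30% | 90% | 27% v 27% | 0 | 3.5% |
| 30% | 80% | 27% v 24% | 3 | 3.8% |
| 30% | 70% | 27% v 21% | 6 | 5.4% |
| 30% | 60% | 27% v 18% | 9 | 8.5% |
| 30% | 50% | 27% v 15% | 12 | 13.6% |
| 50% | 90% | 45% v 45% | 0 | 3.0% |
| 50% | 80% | 45% v 40% | 5 | 4.2% |
| 50% | 70% | 45% v 35% | 10 | 7.9% |
| 50% | 60% | 45% v 30% | 15 | 15.1% |
| 50% | 50% | 45% v 25% | 20 | 26.4% |

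Example: 0.50 × (0.90 − 0.70) = 0.10. In patients, 0.45 × 40 = 18 of 40 recorded with THU-Dec and 0.35 × 20 = 7 of 20 in control, where equal capture would have given 0.45 × 20 = 9 of 20. With a modest deficit (80% capture) the effect on testing is slight. What shifts is the descriptive rates.

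**The case against.** The strongest reply is that Appendix II is a dosing record, still partly template text, and that no section makes it a source of adverse events. A comment enters the record only if an investigator takes it up, through a process common to both arms. If the comments go unused, or the two-weekly review is thorough, capture may be equal and there is no bias. This stands. The effect is conditional, and the table shows only what assumed capture rates imply.

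The consequences are also limited. Safety is a secondary, descriptive endpoint, and Section 3.2 calls the group comparisons mainly exploratory and low in power. The early stopping rule in Section 6.5 concerns removals for grade 3/4 toxicity in the THU-Dec arm, and no decision rule depends on a between-arm rate of mild symptoms. Any bias would make the investigational combination look worse. That also stands, although an overstated toxicity rate is still a wrong answer to a stated objective.

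Some stronger readings are tempting, and the documents do not support them:

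- A reader might infer that control-arm events depend on memory alone. Sections 8.2.1 and 8.2.3 include examination and clinical observation, on the same calendar in both arms.
- A reader might see instruction 4 as a breach of Section 8.2.1. That section rules out asking about specific events, whereas instruction 4 is open and names no symptom.
- A reader might take Section 6.2 to say that no non-haematologic toxicity is expected from THU-Dec. It speaks there only of nausea, vomiting and diarrhea, as the reason for giving no pre-medication.

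**Conclusion.** The asymmetry is real: one arm has a written side-effect prompt that is carried to each visit, and the protocol describes none for the other. If staff use the comments, symptomatic low-grade events may be recorded more fully with THU-Dec, and the by-arm tables of Section 12.2(c) may lean towards more apparent THU-Dec toxicity.

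A reader might go further and conclude that capture is in fact more complete in that arm. The documents do not show this. The direction is what one would expect, and the size is unknown. Under the assumed range above, the gap runs from 0 to 12 points at 30% true incidence and from 0 to 20 points at 50%. Objective response, the two-stage rule and laboratory adverse events are untouched. This is a limited weakness in a secondary, descriptive comparison, and worth correcting because the correction is cheap.

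**What to change.** Keep the Comments column in the capsule diary, because it gives between-visit safety information on an investigational combination. Give nivolumab-alone patients the same four-week side-effect comments sheet, with the same instruction to bring it to each visit, and state in Section 8.2.1 how written comments in either arm are reviewed and entered.

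For patients already treated, flag on the adverse-event form any event known only from the diary, and present the by-arm tables of Section 12.2(c) with and without those events.

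The cost is one extra form for about 20 patients and one source flag. It does not remove reporting differences that come from patients and staff knowing the treatment, and these should be acknowledged when the tables are read.
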